**Screening Procedures:** Using a prepared script for consistency, potential participants will be screened for eligibility at the initial contact. See above inclusion and exclusion criteria. The potential participants will be asked if they have a diagnosis mTBI stemming from military experiences and currently experiencing chronic headaches, insomnia and attention issues; are either a male or female OEF-OIF-OND Veterans between the ages 18 to 65, in addition, females will be asked if they are pregnant or intend to be in the next 8 months; are able to read and write English; are able to comprehend what they read; and are able to follow directions. In addition, they will be asked if they are able to comply with study visit schedule. The Veteran will be questioned to ensure understanding of the purpose of the study. Female Veterans will be informed that if they become pregnant during the intervention phase of study they will be removed from active engagement with an intervention but will be followed through the course of the study and will complete the assessments.

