**Challenges and Alternative Strategies:** Obtaining the required number of participants and retaining participants are concerns for most studies. In February 2019 there were 533 OEF-OIF-OND Veterans with mTBI confirmed by a level 2 evaluation at PIHCS and a potential of over 80 more will be enrolled by December 2019 (the projected timeframe of recruitment for this study to begin) enrolling up to 100 to meet the sample size of 72 Veterans (or about 12% of the projected population) is highly feasible. Inclusion of Veterans who receive their mTBI diagnosis from the DoD or from community providers will increase the pool of eligible participants. These are young, otherwise physically healthy and motivated Veterans who are seeking novel approaches to address their health issues. We are confident that we will be able to recruit 72 for participation over the course of the recruitment period. It is conservatively estimated that 40 letters will need to be mailed out and 40 phone calls made each week in order to fulfill recruitment goals. Adjustments to this schedule will be made as needed to complete recruitment on time. In addition, new mTBI patients will be directly recruited from the mTBI clinic by the providers who perform initial evaluations. However, in the unlikely event that the enrollment numbers are not met, it may become necessary to extend recruitment to the community to obtain the sample size. In addition, completion of 20 sessions of NFB and all 4 assessments may be a challenge to the study's success. This clinical study involves active participation of the Veteran volunteers over a 3-4½ month period. In order to determine the efficacy of NFB, the required number of participants must complete the entire trial and assessment sessions. Attrition rates for NFB have been between 10- 30% as demonstrated in a previous NFB studies. Conservatively we are planning up to a 28% attrition rate. In order to enhance retention over the course of the study, this study will compensate participants for their parking, gas and time (\$27.00 gift card). All subjects will receive payment for the pre, mid, post and follow-up assessment sessions, for a total of \$225.00 in gift cards per subject. The remuneration for the assessments, in the form of gift cards, will be given in a graduated manner to enhance completion rates to include the 2-month follow-up assessment session. Each of the four assessment sessions will take approximately 2.5 hours of time and each subject will receive a \$25 gift card for the baseline assessment, a \$50 gift card at midpoint of treatment and completion of treatment and a \$100 gift card for the 2-month follow-up assessment session. In addition, subjects in the intervention group will receive a \$27 gift card, for gas, time, and parking each time they complete an NFB and assessment session. Each subject in the intervention group will complete 20, one hour, sessions over an 8-10-week period; receiving two-three sessions weekly. Subjects in the post control intervention group, will receive compensation of a \$27 gift card for gas, time and parking for the 20 NFB and assessment session and a \$50 gift card at midpoint of treatment and completion of treatment and a \$100 gift card for the 2-month follow-up assessment session. The gift cards (electronic claim codes) will be housed in a password-protected research project file on the R-drive within the VA server, and carefully tracked by the research coordinator. Gift cards will be distributed in person or alternative method (e.g., US Postal Service, electronic communication). If distributed in person, each participant will indicate that he or she received the gift card on a tracking spreadsheet and it will be

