**Mid (4-6-week), End of Treatment (8-10-week) and 2-Month Follow-up Assessment Sessions (2.5 hours each session):** As above in the baseline assessment, participants will be given preparation instructions to ensure optimum test results. Participants will be instructed to have adequate rest the night before, and to have eaten a regular meal or snack prior to the assessment sessions. There will be an attempt to schedule all sessions at the same time of day for each individual participant, during a period of maximum alertness. One of the tests, the attention QIKtest will be administered early in the assessment session to minimize test fatigue. The participants will also complete several other questionnaires (see Table 5) during these 3 assessment sessions. In addition, the participants will indicate any changes on the demographic form, including changes in pregnancy status (or plans to become pregnant in the next five months) co-morbid health issues, participation in co-occurring classes or therapies and medications. Although the total time for completion of the questionnaires is estimated to be 120 minutes, a 2.5-hour time frame is given for rest periods, water break, slow test takers, and the answering of any questions the participants may have. Should a participant be unable to complete any assessment visit in person, the questionnaires may be mailed to the participant and mailed back at no cost to the participant. Decision to mail the questionnaires will be made by the study team on a case-by-case basis. The QIKtest cannot be mailed therefore this missing data point will be accounted for statistically at final analysis. Instructions will be mailed with the packet. See Appendix B for an example of the general information to be sent to the participants.

**Participation Termination by the Principal Investigator:** Possible reasons for study participation termination by the PI without concurrence by the participant include: concern for the individual's health and/or safety and participant non-compliance with study procedures (e.g., excessive number of missed NFB and/or assessment appointments; non-responsive to outreach attempts for rescheduling; non-responsive to control group phone calls.) Participants will be informed of this decision either in person, via telephone, or via letter. Participants who are terminated could enroll at a later date if they desire. However, the research team will review these requests on a case-by-case basis.

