## Statistical and Data Analysis Plan

The analyses will be conducted based on intention-to-treat principle (Friedman, Furberg, DeMets, 2010) where participants are analyzed according to their group assignment regardless of the treatment received (e.g., switching treatments or poorly adhering to assigned treatment). Patient demographics will be presented using frequencies and percentages for categorical variables and means and standard deviations for continuous variables. Although balance between intervention arms will be guaranteed by randomization, there may be unmeasured confounding. Two sample t tests or chi-square tests will be conducted to investigate potential confounding effects on demographic variables.

For each hypothesis, first two sample t-tests will be utilized to assess the effect of NFB intervention at each time. Then, a repeated-measures analysis of variance (ANOVA) will be implemented for the outcome variable that shows significant group effect. The mixed effects model will include group (between-factor), time (within-factor), and the interaction between group and time as fixed effects. From this model, the interaction will allow the testing of whether longitudinal trajectory is associated with group assignment. The longitudinal trajectory from baseline, 4-6-week and 8-10-week to 2-month follow-up, for each outcome of interest will be investigated in this model accounting for covariance structure (e.g., AR(1)) within participants. This determines the rate of improvement during the course of the intervention. Any baseline subject characteristics found to differ between groups as covariates to assess the impact of the baseline covariates on the effectiveness of the intervention over the course of the study will also be included if needed].

The outcomes of interest for each hypothesis are clinically significant:

- 1) Reduction in frequency, severity and/or impact of headaches: HIT-6 and NEUROQOLTBI
- 2) Improvement of perceptions of quality of sleep and insomnia severity: ISI and NEUROQOLTBI Sleep disturbance
- 3) Improvement in attention function: QIK-Test
- 4) Improvement in the quality of life: QOLIABRI and NEUROQOLTBI Satisfaction & Participation in roles and activities

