## 5) Improvement in the general physical and emotional symptoms: GSI, DASS21, PHQ9, PSL-5 and NEUROQOLTB Positive affect and wellbeing.

As a secondary analysis, a per-protocol analysis will investigate the effect of the intervention in participants that adequately adhere to the intervention, e.g., participants that attend over half of the treatment sessions versus participants attend less half of the treatment sessions. For all analyses, model assumptions will be evaluated with graphical and formal statistical tests such as Kolmogorov-Smirnov goodness-of-fit test. If there is marked nonlinearity or non-normality, transformation of the dependent variable or using a different link function such as the log link function will be considered. All analyses will be done in SAS version 9.4 on a non-VA Computer with two-tailed tests and P-value < 0.05 will be considered statistically significant.

Other statistical analyses not run by the biostatistician will be completed by the research team within the VA Informatics and Computing Infrastructure (VINCI) workspace.

**Power:** Power: Literature on NBF studies of patients with TBI have reported dropout rates ranging from 10% to 30% (Nelson & Esty, 2012; Zoeful, Huster, & Herrmann, 2011). Assuming a dropout rate of 28% and a moderate autocorrelation of 0.6 among repeated measures, this sample size will ensure to detect at least significant difference of 0.49 standard deviation with a power of 80% in the NFB intervention group compared to the control group with two-tailed significance level of 0.05 based on Diggle's et al (2002) approach for 4 repeated measures. This indicates that differences of less than 15% can be detected for HIT-6 (5.8% based on Cerritelli, 2015) and QOLABRI (13.8% based von Steinbuechel et al, 2016) and less than 26% for ISI (17.9% based on Nguyen, 2017) and DASS21 (19.7% based on Arundine et al., 2012) questionnaires. Thus, differences of 15% to 25% in the study instruments would be clinically significant. In addition, this study will detect a difference of at least 0.67 standard deviation if multiple testing is adjusted using FDR, which also provides a moderate effect size.

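### The PI may end study participation for poor adherence with no assurance that outcome assessments continue, so the planned intention-to-treat comparison may be selected on adherence.

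*Combined protocol and SAP*

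**What the plan says.** The paragraph on participation termination by the PI, under Study Procedures for Enrolled Participants, begins: "Possible reasons for study participation termination by the PI without concurrence by the participant include". Besides health or safety, it lists "participant non-compliance with study procedures (e.g., excessive number of missed NFB and/or assessment appointments", failure to respond to rescheduling attempts, and being "non-responsive to control group phone calls". No number defines excessive. The paragraph is silent on whether assessments continue. It adds: "Participants who are terminated could enroll at a later date if they desire", subject to case-by-case review.

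The Statistical and Data Analysis Plan commits to intention to treat, analysing participants by assigned group "regardless of the treatment received (e.g., switching treatments or poorly adhering to assigned treatment". Its secondary per-protocol analysis compares "participants that attend over half of the treatment sessions versus participants attend less half of the treatment sessions".

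Pregnancy is handled differently. Under Screening Procedures, and again under Vulnerable populations, a woman who becomes pregnant is to be "removed from active engagement with an intervention but will be followed through the course of the study and will complete the assessments".

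Three other places matter. Neurofeedback Treatment Sessions names the PI as one of the NFB specialists and as supervisor of the others. Enrollment is defined as complete at randomization. Data Protection records that participant procedures were complete as of March 2025.

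**The concern.** Intention to treat needs outcomes from everyone randomised, and above all from those who adhered badly. A rule that ends study participation because of poor adherence can remove the people whom the analysis plan promises to include. If removal is more frequent in one arm, or takes out people with a different prognosis, the remaining groups are no longer the randomised groups.

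Three features add to this. The grounds are open-ended and rest with a person who delivers the intervention in an unblinded trial. The occasions for non-compliance differ by arm: 20 in-person NFB sessions against eight 15-minute calls. The first analysis step is a two-sample t-test at each time, which uses only those observed at that time, and its result decides which outcomes go on to the mixed model.

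At stake is whether a reader can take the reported comparison as the intention-to-treat result. The low-attendance group in the per-protocol analysis may be depleted by the same rule.

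**Working it through.** **1. The provisions side by side**

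| Provision | Intervention stops? | Assessments continue? |
|---|---|---|
| Pregnancy (Screening Procedures; Vulnerable populations) | Yes | Yes, stated |
| Termination for non-compliance | Study participation ends | Not stated |
| Intention to treat | Not relevant | Needed from poor adherers |
| Per-protocol comparison | Not relevant | Needed from those attending less than half |

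The protocol separates stopping the intervention from stopping follow-up in one place and not in the other. That terminated participants lose later assessments is an inference from the words used and from this contrast. No sentence states it.

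**2. The plan's own figures**

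Dropout: 72 / (1 − 0.28) = 100, which reproduces the recruitment figure. This allowance replaces the number lost; it does not protect against selective loss.

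The detectable difference of 0.49 SD is not needed for this point. With 36 per arm, four measures and correlation 0.6, the variance factor for an average over time is (1 + 3 × 0.6)/4 = 0.7 under equal correlation. The two-sided figure is √[2 × (1.96 + 0.8416)² × 0.7 / 36] = 0.55 SD. With AR(1) correlation the factor is 0.592 and the figure 0.51 SD. One-sided with equal correlation, replacing 1.96 by 1.645, it is 0.49 SD. So the stated value is not reproduced under the stated two-tailed test. That is a separate matter.

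**3. Bias from selective loss**

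Let a share q of an arm be removed, and let those removed have a mean outcome worse by g SD than those kept. The whole arm's mean is then the kept mean minus q × g, so analysing only those kept flatters the arm by q × g. With the same g in both arms, the between-arm bias is (q_NFB − q_control) × g.

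The removal shares and g are assumptions; the documents give neither. The 28% borrows the planned all-cause attrition as a high value.

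| Removed, NFB vs control | g = 0.25 SD | g = 0.5 SD |
|---|---|---|
| 28% vs 28% | 0 | 0 |
| 28% vs 14% | 0.14 × 0.25 = 0.035 | 0.14 × 0.5 = 0.07 |
| 28% vs 0% | 0.28 × 0.25 = 0.07 | 0.28 × 0.5 = 0.14 |

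**4. Effect on the two-sided 5% error rate**

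Error = 1 − Φ(1.96 − b/SE) + Φ(−1.96 − b/SE), with bias b and 36 per arm.

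| Bias b (SD) | One time point, SE = √(2/36) = 0.236 | Average of four measures, SE = √(2 × 0.7/36) = 0.197 |
|---|---|---|
| 0.035 | 5.3% | 5.4% |
| 0.07 | 6.0% | 6.5% |
| 0.14 | 9.1% | 10.9% |

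**The case against.** The case on the other side has real force.

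- **The clause is discretionary.** It lists possible reasons and sets no threshold. It does not say that data already collected are discarded, nor that assessments stop. This stands, and is why the point is that later outcomes are not assured.
- **Two grounds apply to both arms:** missed assessments and failure to respond to rescheduling. People in these categories would largely be missing anyway. This stands. What differs by arm is the opportunity for removal; no removal rates are given.
- **A mixed model can use partial data.** True, but in this plan it is fitted only to outcomes that already show a group effect in the t-tests, which do not use earlier observations from people absent later. Attendance is not among the listed model terms, and no missing-data method is given beyond a remark about the QIKtest.
- **Retention is well supported** by reminders, flexible hours, graduated payments and mailed questionnaires. The statement that "the required number of participants must complete the entire trial and assessment sessions" reads as a retention goal, not as a rule for dropping people.

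A reader might go further and infer a large overstatement. If all 28% planned attrition were NFB non-adherers removed, who gained nothing, while the rest gained 0.49 SD, the effect in everyone would be 0.49 × 0.72 = 0.35 SD against 0.49 SD observed, an excess of 1/0.72 − 1 = 39%. The documents do not support this. The 28% is all-cause attrition for the whole trial, zero benefit in non-adherers is an assumption, and control-arm loss would have to be unrelated to outcome. That calculation also gives no bias when NFB has no effect.

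Nor do the documents show that the low-attendance group would be emptied: the termination rule has no session count, and terminated participants may have baseline and mid-treatment data.

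**Conclusion.** The termination rule and the analysis plan need to be reconciled. The protocol permits removal of poor adherers from the study without assuring their later outcomes, while the analysis plan claims those outcomes for intention to treat and for the attendance comparison. The t-tests at each time may therefore be selected on adherence.

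The amount and even the presence of bias are unknown. The 0.035 to 0.14 SD range rests on the assumed removal shares and prognosis gap, and on those removed having no later data. It leans towards NFB only if removal is commoner in the NFB arm and those removed would have done worse. Re-enrolment adds a gap: since enrollment is completed by randomization, someone who returns might be allocated twice, and no rule says how that person is counted.

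This should be fixed. It does not by itself invalidate the trial, and because participant procedures are complete, no change can now recover missed assessments.

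**What to change.** Reconcile the termination paragraph with the analysis plan. Separate the end of NFB sessions or calls for non-compliance from the end of outcome assessment, as is done for pregnancy. Leave the health and safety ground there, and its counterpart under Crisis Procedure, as they are.

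For the present data, before the analysis:

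1. Report terminations by arm, reason and time.
2. Keep every randomised participant and all collected assessments in the intention-to-treat set. Count anyone who re-enrolled once, under the first allocation.
3. Fit the mixed model to all available data for every outcome, not only those that pass the t-test step. Add a sensitivity analysis that assumes worse outcomes for terminated participants, for example by 0.25 and 0.5 SD.
4. Describe the t-tests at each time as available-case comparisons, not as full intention-to-treat results.

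The cost is a short addition to the analysis plan, a little more analysis, and a less favourable label on the t-tests. No further participant contact is needed.

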## Statistical and Data Analysis Plan

The analyses will be conducted based on intention-to-treat principle (Friedman, Furberg, DeMets, 2010) where participants are analyzed according to their group assignment regardless of the treatment received (e.g., switching treatments or poorly adhering to assigned treatment). Patient demographics will be presented using frequencies and percentages for categorical variables and means and standard deviations for continuous variables. Although balance between intervention arms will be guaranteed by randomization, there may be unmeasured confounding. Two sample t tests or chi-square tests will be conducted to investigate potential confounding effects on demographic variables.

For each hypothesis, first two sample t-tests will be utilized to assess the effect of NFB intervention at each time. Then, a repeated-measures analysis of variance (ANOVA) will be implemented for the outcome variable that shows significant group effect. The mixed effects model will include group (between-factor), time (within-factor), and the interaction between group and time as fixed effects. From this model, the interaction will allow the testing of whether longitudinal trajectory is associated with group assignment. The longitudinal trajectory from baseline, 4-6-week and 8-10-week to 2-month follow-up, for each outcome of interest will be investigated in this model accounting for covariance structure (e.g., AR(1)) within participants. This determines the rate of improvement during the course of the intervention. Any baseline subject characteristics found to differ between groups as covariates to assess the impact of the baseline covariates on the effectiveness of the intervention over the course of the study will also be included if needed].

The outcomes of interest for each hypothesis are clinically significant:

- 1) Reduction in frequency, severity and/or impact of headaches: HIT-6 and NEUROQOLTBI
- 2) Improvement of perceptions of quality of sleep and insomnia severity: ISI and NEUROQOLTBI Sleep disturbance
- 3) Improvement in attention function: QIK-Test
- 4) Improvement in the quality of life: QOLIABRI and NEUROQOLTBI Satisfaction & Participation in roles and activities

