
cosigned by a research team member for verification purposes. If the gift card(s) is mailed, staff will send the gift card(s) using a return receipt method (e.g., certified mail) to ensure delivery to the participant. A letter will be included with the mailing. The letter will list the visit date(s) and type (e.g., assessment, treatment) associated with the gift card(s). Staff will maintain contact with the participant (e.g., phone call advising of mailing date) to help ensure successful delivery. The return receipt will be filed with the participant's study chart. If the gift card(s) is delivered electronically, the message will include a table with a list of the visit date(s) and type (e.g., assessment, treatment) associated with the gift card(s). The message will ask the participant to reply to the message to acknowledge receipt of the gift card(s). The message will be saved and filed with the participant's study chart.

In addition, interventions will be offered at hours and days that would enable Veterans who work to participate. Phone calls will be made as session reminders, the week and day before as well as on the day of appointment. In addition, a paper monthly calendar with the appointments indicated that can be hung on the wall will be given as well as an appointment card at the end of each session. In addition, those in the control group, will be offered NFB training, after they complete the control group requirements.

**Outcome Measures:** Outcome measures will be used to compare the results of the NFB intervention and control group. Statistical tests and analyses will be conducted to determine the existence of statistical differences between the intervention and control group measures and on the measures at pre-treatment, midpoint, and immediate post treatment for determination of clinical improvement.

To determine the impact of NFB, the following assessment tools (see Table 4) will be administered at baseline, 4-6 weeks (midpoint of treatment), and 8-10 weeks (conclusion of treatment) and 2 months following completion to the control and intervention mTBI groups.

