#### Additional Baseline Instruments

9	Patient Health Questionnaire-9 PHQ-9	Reliability: Cronbach's Alpha 0.96 Validity: $r = 0.62- 0.90$ $p < .001$	PHQ-9 is a nine-item depression self-report module from the full Patient Health Questionnaire. Scores range from 0-27. (9 items, 2-5 min)	Objective 5. To determine the presence of an often co-occurring health issue, depression, with mTBI prolonged symptoms. Estimates as high as 34% of mTBI SMs with depression.
10	Posttraumatic Stress Disorder Checklist PCL-5	Reliability: Cronbach's Alpha 0.89 Validity: Sensitivity 84% Specificity 72%	The PCL-5 is a 20-item questionnaire, corresponding to the DSM-5 symptom criteria for PTSD. The wording of PCL-5 items reflects both changes to existing symptoms and the	Objective 5. To determine the presence of an often co-occurring health issue, PTSD, with mTBI. Estimates as

		r = 0.89	addition of new symptoms in DSM-5. (20 items, 5-10 min)	high as 60% of SMs with mTBI with PTSD.
--	--	----------	---	---

Table 5 depicts the schedule of administration for each of the tools used in this study.

Table 5. Assessment Tool Schedule of Administration by Group							
Assessment Tool		Schedule of Administration					Group
No	Abbreviated Name	Initial: at -1 week	Mid: at 4-6 weeks [±1 week]	End: at 8-10 weeks [±2 weeks]	2-Month Follow-up	Other	Intervention and Control
1	HIT-6	x	x	x	x		x
2	ISI	x	x	x	x		x
3	QIKtest	x	x	x	x		x
4	NEUROQOL TBI	x	x	x	x		x
5	QOL ABRI	x	x	x	x		x
6	GSI	x	x	x	x	At each session*	x
7	Demographic Data Form**	x	x	x	x		x
Additional Baseline Instruments							
8	PHQ-9	x	x	x	x		x
9	PCL-5	x	x	x	x		x
10	DASS-21	x	x	x	x		x
		* An abbreviated symptom inventory based on participant's primary symptoms will be administered at each NFB session to assist with treatment planning. **Current medications, diagnoses, and treatments that were indicated initially on Demographic data will be checked at the 3 assessment sessions to see if any deletions or additions occurred during course of study intervention.					

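### The covariance structure of the longitudinal model is left open, and its only example, AR(1), ignores visit gaps of about 5, 4 and 9 weeks

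*Combined protocol and SAP*

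**What the plan says.** The Statistical and Data Analysis Plan has two steps for each hypothesis. In the first, "first two sample t-tests will be utilized to assess the effect of NFB intervention at each time". Outcomes that show a significant group effect then go to a repeated-measures model with "group (between-factor), time (within-factor), and the interaction between group and time as fixed effects". The plan states the purpose of that model: "the interaction will allow the testing of whether longitudinal trajectory is associated with group assignment". On within-participant correlation it says only "accounting for covariance structure (e.g., AR(1)) within participants". It gives no final structure, selection rule, random effect, robust standard error or degrees-of-freedom method.

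Under Outcome Measures, the assessments after baseline are set at "4-6 weeks (midpoint of treatment), and 8-10 weeks (conclusion of treatment) and 2 months following completion". Table 5 adds windows of ±1 week at mid-treatment and ±2 weeks at end of treatment.

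The Power paragraph assumes "a moderate autocorrelation of 0.6 among repeated measures" and uses a published "approach for 4 repeated measures". It does not say whether the 0.6 holds for every pair of visits or only for adjacent ones.

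**The concern.** Taking the middle of each window and counting two months as about 9 weeks, the visits fall near weeks 0, 5, 9 and 18. AR(1) over visit number uses one correlation, ρ, for every pair of neighbouring visits and ρ² and ρ³ for wider pairs. It therefore treats the 9-week gap after training like the 4-week gap during it, and it forces the baseline-to-follow-up correlation down to ρ³.

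Model-based standard errors of group-by-time contrasts are built from these correlations. Two contrasts that readers will look for are change from baseline to follow-up, and change from end of treatment to follow-up, which shows whether a benefit lasts. If the structure does not fit, p-values and intervals for such contrasts can be too cautious or too optimistic. Leaving the structure open also allows it to be chosen after the results are seen, for each of 13 outcome scales.

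**Working it through.** **Inputs.** 36 completers per arm (Accessible Population section); four visits; two-sided 5% level; correlation 0.6 (Power paragraph); visits at weeks 0, 5, 9 and 18. The true correlation pattern is not in the documents, so two patterns are assumed. Variances are equal (SD = 1) and data complete.

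**The plan's own figure.** For a time-averaged difference, d = (z_α + z_power)·√(2f/36), where f is the mean of the 4×4 correlation matrix and z_power = 0.842 for 80% power.

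| Pattern | f | d, two-sided 0.05 | d, one-sided 0.05 |
|---|---|---|---|
| 0.6 for all pairs | 0.700 | 0.552 | 0.490 |
| AR(1), 0.6 | 0.592 | 0.508 | 0.451 |
| Decay of 0.6 per 5 weeks | 0.561 | 0.494 | – |

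The stated 0.49 SD is matched by constant correlation only at one-sided alpha, whereas the plan says two-tailed. At two-sided alpha, calendar-time decay comes close. The figure therefore cannot show which structure was assumed.

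**Standard error of a contrast.** For the difference between arms in the change between two visits with correlation r, SE = √{2·2(1 − r)/36}. The model SE uses the AR(1) value of r and the true SE uses the assumed one. Test size is 2{1 − Φ(1.96 × model SE/true SE)}. With equal variances, the fitted AR(1) ρ is the average of the three adjacent-visit correlations.

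**Scenario A: true correlation 0.6 for all pairs.** The fitted ρ is 0.6.
- Follow-up minus baseline: the true r is 0.6, so the SE is √(1.6/36) = 0.211. The model r is 0.6³ = 0.216, so the SE is √(3.136/36) = 0.295. The ratio is 1.40 and the size 0.6%.
- Power for 0.49 SD on this contrast: Φ(0.49/0.2108 − 1.96) = 64% with the right SE. With the AR(1) SE it is Φ{(0.49 − 1.96 × 0.2951)/0.2108} = 34%.
- End of treatment minus baseline: the model r is 0.36 and the SE 0.267 against 0.211. The ratio is 1.26, the size 1.3%, and power for 0.49 SD is 44% instead of 64%.
- Contrasts between adjacent visits are right.
- If the constant correlation is 0.5 or 0.7 instead, the follow-up-minus-baseline ratio is 1.32 or 1.48.

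**Scenario B: correlation decays with time, 0.6 per 5 weeks.** Adjacent correlations are 0.6000, 0.6^(4/5) = 0.6645 and 0.6^(9/5) = 0.3987. The fitted ρ is their mean, 1.6632/3 = 0.554.
- Follow-up minus end of treatment: the true SE is √{4(1 − 0.3987)/36} = 0.258 and the model SE √{4(1 − 0.554)/36} = 0.223. The ratio is 0.86 and the size 9.2%.
- Mid-treatment and end of treatment minus baseline: SEs are 5% to 7% too large.
- Follow-up minus baseline: the ratio is 0.99, about right.
- With other visit times within the stated weeks and decay of 0.6 per 5 or 6 weeks, the follow-up-minus-end ratio is 0.84 to 0.88 and the size 8.5% to 9.8%.

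**Overall 3-df interaction test** (400,000 simulated draws per case). Type I error is 4.4% in scenario A and 5.4% in scenario B. For a constant 0.49 SD effect at all three visits after baseline, power in scenario A is 66% with the right structure and 48% with AR(1).

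**The case against.** Four points on the other side carry weight.

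- **AR(1) is only an example.** A reader might infer that the plan commits to equal spacing. It does not: an unstructured or time-based covariance already fits the wording. The plan also speaks of a mixed effects model, and a random intercept plus AR(1) would remove the error in scenario A, though not in scenario B. This stands, so the defect is an open choice with an unsuitable example.
- **The power calculation.** A reader might infer that it assumed 0.6 for every pair and so contradicts AR(1). The documents do not support that. The Power paragraph names no structure, the word autocorrelation can equally mean the lag-1 value of an AR(1) process, and the 0.49 SD does not settle it.
- **The interaction test.** A reader might infer that the planned longitudinal test is invalid. Its type I error stays near 5% in the cases checked; what it can lose is power.
- **The t-tests come first.** They use one visit at a time, do not depend on the covariance, and decide which outcomes reach the model. They are unaffected.

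The plan also promises to evaluate model assumptions for all analyses. Its stated checks and remedies concern linearity and distribution, so they would not pick up a wrong covariance.

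**Conclusion.** The point holds in a limited form: the covariance is not pre-specified, and the only structure named suits the visit schedule poorly. If AR(1) were used, single contrasts could have standard errors from about 40% too large (follow-up minus baseline, constant correlation 0.6) to about 14% too small (follow-up minus end of treatment, decay of 0.6 per 5 weeks). The first costs power; the second raises the false-positive rate to about 9%. The overall interaction test would keep its level but could fall from 66% to 48% power in the first case.

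These sizes rest on assumed correlations, equal variances, 36 per arm and complete data. Up to 28% dropout is planned for, and with missing visits the covariance also influences the estimates themselves; that effect was not quantified. This is a cheap improvement. It does not show that the trial's main comparisons are wrong.

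**What to change.** In the Statistical and Data Analysis Plan, replace the AR(1) example with an unstructured covariance over the four visits, fitted by REML with Kenward-Roger degrees of freedom. Name one fallback in case of non-convergence, such as heterogeneous Toeplitz, or spatial power using each participant's actual weeks. The Data Protection section says participant procedures were complete as of March 2025, so the change should be made and dated before outcomes are compared by arm. The documents do not say whether that comparison has begun.

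The cost is a change of wording and 10 covariance parameters instead of 2 per outcome, eight more. That is estimable with about 72 participants and four visits, and the planned SAS 9.4 can fit it. Stating in the Power paragraph which pairs of visits the 0.6 refers to would also remove the ambiguity there.
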